11.6 Screening and cohort enrollment procedures

HIV POSITIVE COHORT

All participants who test HIV positive will be invited to enroll in the SMART design adaptive intervention pilot. Prior to enrollment in the linkage intervention, all participants who test HIV positive will be asked if they are willing to receive cell phone text messages to remind them to link to care, or if they would be willing to respond to cell phone text messages with no more than 15 questions every 3 months for 12 months. If so, they will be given a low-cost cell phone.

All participants who test HIV positive, give consent and are eligible, will be enrolled in the HIV positive cohort.

HIV Positive Cohort Eligibility Requirements:

Inclusion Criteria:

- Meets general eligibility criteria.
- Registered with the GIRLS study and assigned a valid Study ID number.
- Previously signed IC or if younger than 18 years of age (and not an emancipated minor) has a parent or guardian who provided consent in addition to their individual assent.
- Resides in the catchment area.
- HIV positive by two (2) rapid tests.
- Willing to receive SMS texts to link to HIV care and treatment services.

11.6.1 Linkage to Care Intervention

We will use an adaptive intervention/SMART trial design methodology to compare the success of a) short message service (SMS) text messaging and b) economic incentive (transport reimbursement worth KSh 400) systems in linking to HIV care and treatment services participants who test positive for HIV (expected N≈108) and require augmented linkage support. The initial intervention (first randomization) is that participants who test positive for

HIV gets a standard referral or standard referral plus an SMS message with instructions on where to seek care. Some participants may engage in HIV care after receiving either the referral or referral plus SMS. Subsequently, the intervention will be tailored so those participants who are not linked to care within 2 weeks after the initial intervention, who will be randomized again to receive either follow-up SMS with linkage encouragement, or a one-time economic incentive to seek care (shown to be effective in previous studies (Handa et al., 2014)). All HIV positive participants enrolled for follow up will receive a motivational SMS with adherence to medication and care messages and an SMS survey at intervals of 3 months for 12 months.

At 12 months, we will follow-up with those participants that tested positive and enrolled in care to measure their viral load to determine whether they have been linked, retained in care and are adhering to treatment. We will also conduct an interview at 12 months to determine barriers and facilitators for linkage to care and treatment.

We will be working with Homa Bay County, Ndhiwa and Mbita health facilities. Participants identified as HIV+ will be referred to Government of Kenya HIV Care centers referred to as Comprehensive Care Centers (CCC) for ART initiation. As previously stated, the GoK is moving towards adopting the WHO's recommended Test and START guidelines; therefore, we will test for CD4 at baseline for clinical staging, counseling and treatment preparation purposes and collect sample (DBS) for viral load at the point of recruitment (community mobile event or home based) for those who test HIV-positive so as to enhance the motivation and information for the HIV+ female youth. Any HIV-positive female who self-reports that she is pregnant will be actively referred for PMTCT interventions and follow-up. Those eligible for ART/PMTCT referral but declining linkage intervention will be offered a declined intervention survey to examine reasons and will be referred to a facility of their choice and support group.

Successful linkage to care is defined as date of first appointment at the HIV clinic (registering for care, and being assigned a patient number). We will work with existing structures at IRDO to verify if and when the participant reached the clinic and entered into care.

Figure 8, Adaptive Intervention.

[figure not shown]

Figure 8: Adaptive Intervention *

* those not enrolled into the HIV positive cohort will be referred for care and treatment at facilities of their choice.

Randomization

Newly diagnosed HIV-positive females identified in our study will be randomized to receive standard referral to link to care or standard referral plus SMS message to link to care. Those that do not successfully link to care will then be re-randomized to receive either a second SMS message or an economic incentive. We will utilize an approach called permuted blocks randomization for participant assignment to the intervention. Permuted block randomization has several advantages, one of which is promoting equal distribution of participants in each group. A list of random allocations will be generated by the study statistician in randomly ordered permuted blocks of either 2, 4, 6, 8 or 12 allocations. The allocation list will be stored in a password protected file which will only be accessible to the study statistician, data manager or project manager.

The field study coordinator will provide a list of study ID numbers of participants needing allocation. The study statistician or data manager will record the unique study identification number and the date of the assignment on the allocation list, and relay the assignment to the field study coordinator. Alternatively, if we find that this is not efficient during implementation of our study, we will pursue other methods, such as using sequentially numbered, sealed envelopes containing participant allocation that may be prepared beforehand (Doig & Simpson, 2005).

We anticipate a total of 108 HIV positive participants to be randomly assigned to either standard referral or standard referral plus SMS at the first randomization. Participants not linked to care after the first randomization will be re-randomized in a 1:1 ratio to receive either another SMS text or an economic incentive.

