15.12 Randomization

Our study is observational in nature, but the Aim 2a adaptive linkage to care intervention does contain a randomization component. Newly diagnosed HIV-positive females identified in our study will be randomized to receive standard referral to link to care or standard referral plus SMS message to link to care. Those that do not successfully link to care will then be re-randomized to receive either an SMS message or an economic incentive. We will utilize an approach called permuted blocks randomization for participant assignment to the intervention. Permuted block randomization has several advantages, one of which is promoting equal distribution of participants in each group. A list of random allocations will be generated by the study statistician in randomly ordered permuted blocks of either 2, 4, 6, 8 or 12 allocations. The allocation list will be stored in a password protected file which will only be accessible to the study statistician, data manager or project manager.

The field study coordinator will provide a list of study ID numbers of participants needing allocation. The study statistician or data manager will record the unique study identification number and the date of the assignment on the allocation list, and relay the assignment to the field study coordinator. Alternatively, if we find that this is not efficient during implementation of our study, we will pursue other methods, such as using sequentially numbered, sealed envelopes containing participant allocation that may be prepared beforehand (Doig & Simpson, 2005).

We anticipate a total of 108 HIV positive participants to be randomly assigned to either standard referral or standard referral plus SMS at the first randomization. Participants not linked to care after the first randomization will be re-randomized in a 1:1 ratio to receive either another SMS text or an economic incentive.

See Section13: Statistical Considerations and Section 18: Data Handling and Record Keeping.

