18. DATA HANDLING AND RECORD KEEPING

18.1 Data Management

18.1.1 Screening IDs, Participant ID Numbers (PTIDs), and unique barcodes

Screening IDs will be assigned to all potential study participants who are approached for enrollment.

- Screening IDs are assigned at the participant's first screening visit, regardless of whether or not the potential participant completes screening for the study.
- Participant Identification Numbers (PTIDs) are assigned at Enrollment and are separate from the Screening ID.
- The Nairobi Office will provide both Screening IDs and PTIDs.

Both Screening IDs and PTIDs ideally will be assigned in sequential order; however, it is recognized that deviations from sequential ordering occur from time to time, e.g., when several potential participants are approached for possible screening or enrollment at the same time.

Pre-printed barcode labels will be procured from a vendor. Study staffer will place a pre-printed barcode label (with a unique barcode number) on the camera and on the self-test kit. Study staffer will then record the barcode numbers on a tracking form to ensure that it links with the participant's study identification number.

The Data Manager/Designee is responsible for maintaining the list of screening IDs and PTIDs and assigning screening IDs and PTIDs to potential participants. The Data Manager/Designee will also maintain the list of the unique barcodes affixed on the self-testing kit and the camera that is assigned to each participant who chooses the self-testing option.

- The Data Manager will enter participant details (age, last-name) into the Participant Tracking Access Database after the participant visits and after he/she has reviewed the information for accuracy and completeness.
- The Data Manager will enter the unique barcode number affixed to the test kit and camera into the Participant Tracking Access Database. He/she will ensure that the barcode numbers are linked to the correct participant identification number. Electronic photos from the camera will be uploaded to a study computer and labeled with the unique camera barcode number. No participant name or other identifier will be attached to these images.

Additional information on organization, types of data, and storage of study files can be found in the SSP.

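### Allocation concealment is not assured against the data manager, who can see unreleased allocations, may enter listed IDs against them in no specified order, and also issues IDs and holds tracking data

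*Combined protocol and SAP*

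**What the plan says.** Section 11.6.1 (Randomization) has the statistician generate the list in "randomly ordered permuted blocks of either 2, 4, 6, 8 or 12 allocations" and store it in a password-protected file "which will only be accessible to the study statistician, data manager or project manager". Requests are grouped: "The field study coordinator will provide a list of study ID numbers of participants needing allocation". Section 15.12 repeats the procedure: "The study statistician or data manager will record the unique study identification number and the date of the assignment on the allocation list", after which the assignment is relayed to the field study coordinator. The same steps serve both randomisations. If this proves inefficient, other methods are allowed, "such as using sequentially numbered, sealed envelopes containing participant allocation that may be prepared beforehand".

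Section 18.1.1 makes the Data Manager/Designee "responsible for maintaining the list of screening IDs and PTIDs and assigning screening IDs and PTIDs to potential participants" and has the data manager enter age and last name into the tracking database. Section 18.1.2 limits access to that database to the data manager and backup/designee, the study coordinator and the principal investigator. Sequential ID order is described there as an ideal with accepted deviations, and it concerns the issue of IDs, not their randomisation.

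Nowhere do the documents say that later entries on the list are hidden, that IDs are taken in order of request, or that an ID is committed before the next allocation is read.

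**The concern.** Concealment requires that whoever attaches a participant to an allocation does not know that allocation beforehand. Here the data manager may open the whole list, may enter the IDs, and holds identifying data on the people behind them. With several IDs waiting and no ordering rule, that person could decide who takes which slot. Only the date of assignment is recorded, so a later audit could not reconstruct the order within a day.

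The pilot contains the study's only randomised comparisons; section 15.12 says "Our study is observational in nature, but the Aim 2a adaptive linkage to care intervention does contain a randomization component". No blinding is described, and at the second stage one arm receives a KSh 400 payment. Section 17.5.1 itself notes that transport cost can be a barrier to care, so well-meaning staff could have a reason to favour some participants. Steering by perceived need or readiness to link would bias the first-stage contrast and the second-stage hazard ratio for SMS versus incentive. No analysis of the recorded data could reliably remove that bias.

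**Working it through.** **Roles side by side**

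| Role | Unreleased list (11.6.1, 15.12) | Enters IDs on list | Issues study IDs (18.1.1) | Tracking database (18.1.2) |
|---|---|---|---|---|
| Statistician | yes | yes | not stated | no |
| Data manager | yes | yes | yes | yes |
| Project manager | yes | not stated | not stated | not listed |
| Field/study coordinator | no | no (sends IDs, receives arms) | not stated | yes |

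Only the data manager has every entry.

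**Size of the randomised comparisons.** First stage: 108 participants, about 54 per arm (section 6). Second stage: 80% of 108 = 86.4, stated as 86 in section 15.11; at 1:1, 43 per arm. The plan's own power figure reproduces. With 60% linked, events = 0.6 × 86 = 51.6. By Schoenfeld's formula at two-sided 0.05 (assumed; not stated for this calculation), detectable HR = exp[(1.960 + 0.842)/√(51.6 × 0.25)] = 2.18, against the stated 2.2. That figure is not in dispute.

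**Room to choose, with the list in view.** With k IDs waiting and the next k slots evenly split, C(k, k/2) pairings are possible: 2 for k = 2, 6 for k = 4, 20 for k = 6. If accrual is even over 12 months (assumed), flow is 108/52 = 2.1 a week at the first stage and 86/52 = 1.7 at the second. Table 1 allows one week to re-randomise, so a typical waiting group would be about two.

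**Effect of steering (illustration, no true effect).** Take eight second-stage participants, four who would link and four who would not. From a balanced split (two of each per arm), moving all four linkers to one arm and all four non-linkers to the other adds 2/43 to one arm and takes 2/43 from the other. The difference shifts by 4/43 = 9.3 percentage points.

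**Prediction without the list.** Assume the five block sizes are equally likely and the guesser always names the arm that is behind. Expected correct guesses in a block of size 2b are b + [2^(2b)/C(2b,b) − 1]/2:

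| Block size | 2 | 4 | 6 | 8 | 12 | Sum (of 32) |
|---|---|---|---|---|---|---|
| Correct | 1.50 | 2.83 | 4.10 | 5.33 | 7.72 | 21.48 |

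21.48/32 = 67.1%. Simulation over 108 or 86 allocations gives about 67%, and a guesser making optimal use of all past assignments does no better. The next arm is certain for only about 1% of participants. These figures need feedback after every assignment. If arms are learned only between batches, the same strategy is right about 59% of the time for batches of two, 61% for three, 57% for four and 58% for five.

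**The case against.** The strongest reply is that much of this is silence rather than stated practice. The file is password-protected, five block sizes are mixed, and each assignment carries an ID and a date. Operating detail may sit in procedures manuals outside these documents. The data manager's office is in Nairobi (section 18.2.1), requests are described as ID numbers, and no participant contact by that role is documented. Steering would therefore need judgement from database records or help from field staff. The pilot is a secondary objective, and linkage is verified from medical records.

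Most of this limits the concern without removing it. A password excludes outsiders, not the person entering IDs. Varied blocks hinder guessing, not reading. Record verification protects outcome ascertainment, not assignment. Small waiting groups reduce the room to choose, but two IDs facing two different arms already offer a choice.

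A reader might infer more than the text supports:
- That tracking staff in general can see upcoming arms. The combination is documented only for the data manager.
- That IDs are in fact matched in no fixed order. The order is simply not specified.
- That all allocations come from one unstratified sequence. The number of lists and any stratification are not stated.
- That envelopes would be held in the field. They are one example of a fallback, are sequentially numbered and sealed, and their location is not given. The gap is opacity, custody and an opening log.
- That coordinators can generally predict the next arm. The figures above show only a moderate advantage.

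**Conclusion.** The gap is real and specific. As written, the access and entry rules do not assure concealment against the data manager at either randomisation. The main risk is selection by someone who can read the list; prediction by others is secondary, at most about 67% correct against 50%, assuming equally likely block sizes and feedback after each assignment.

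The 9-point shift is an illustration of sensitivity with 43 per arm, not an expected bias. It rests on a balanced starting split and on successful deliberate steering of eight participants whose outcomes were correctly foreseen. Nothing in the documents suggests that anyone intends this. Sample size and planned analysis are unaffected. The change is still worth making, because it costs little and protects the only randomised evidence in the study.

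**What to change.** Amend the randomisation text in sections 11.6.1 and 15.12:

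1. Limit access to the unreleased list to the study statistician and a named backup who has no ID-assignment, tracking or outcome role. Remove the data manager and project manager.
2. At both randomisations, allocate one ID at a time in time-stamped order of request, with each ID committed before the next allocation is read. Record time as well as date.
3. If the envelope fallback is kept, require opaque envelopes held by an independent person, opened in sequence only after the ID is written on them, and logged.
4. If a database releases allocations instead, state that the data manager cannot see later entries. Section 18.2.1 houses the study database in the data manager's office, so loading the list there without that restriction would recreate the problem.

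The cost is protocol wording and naming a backup; a database route would also need set-up work, which the documents do not allow one to size. The downside is slightly less flexibility when the statistician is unavailable, which the backup covers.

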Study Intervention Description	
The following will be offered to all female youth (N=1200):
 
 (1) HIV Testing Services (HTS) via home-based or community based recruitment strategies (2) HIV testing approaches that females can choose from include: (a) oral fluid HIV self-testing (OraQuick ADVANCE® Rapid HIV-1/2 Antibody Test, OraSure Technologies) at their convenience; (b) staff-aided testing at home/mobile site; and (c) a referral to a health care facility where HIV testing will be done by a health care provider (standard facility-based HTS) (3) Behavioral survey at baseline visit (4) SMS HIV test experience satisfaction survey (5) Staff-administered questionnaire about self-testing for females who choose self-testing option. 
For all HIV positive females:
 
All HIV positive females will receive the following;
 
 (1) Point of care (POC) CD4 cell count at baseline (2) Viral load testing using dried blood spot (DBS) at 0 and 12 months (3) Referral for care and treatment; Adaptive linkage to care intervention. All HIV positive participants (N≈108) will be randomized to receive standard referral (N≈54) or standard referral plus SMS message (N≈54) to link to HIV care and treatment services; those who do not link to care within 2 weeks will be re-randomized in a ratio of 1:1 to a second SMS message or a one-time economic incentive to link to care.

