Adaptive Intervention Pilot: Descriptive statistics and survival plots will be used to characterize occurrence and timing of linkage among girls responding to the initial SMS message and girls in each augmented treatment condition. Survival analysis (Singer & Willett, 2003; Therneau & Grambsch, 2000) will determine which approach to augmenting linkage – continued SMS or economic incentives – is more effective in linking female youth newly diagnosed with HIV to care sooner. Using the Cox Proportional Hazards Model, difference in the likelihood and timing of linkage between treatment conditions will be quantified with an interval estimate of the hazard ratio. Median time to linkage also will be estimated and compared across treatment conditions.

Cost Effective Analysis

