With this estimate of the expected percentage of girls with newly diagnosed HIV infection, we asked how small of an increase in the odds of newly diagnosed HIV infection could be detected with 80% power when community-based recruitment is compared to home-based recruitment. With 600 youth recruited by each strategy, power is 80% to detect an odds ratio of 1.67, in other words, a modest increase from 9% to 14% newly diagnosed with HIV infection. When comparing testing approaches, and assuming an equal proportion of girls prefers each approach and testing approach does not interact with recruitment strategy, power is 80% to detect an odds ratio of 1.85. If there is an interaction between recruitment strategy and testing approach, when comparing

testing approaches within a recruitment strategy (i.e., estimating simple main effects), power is 80% to detect an odds ratio of 2.32.

These calculations show the proposed sample size (N=1200) is capable of detecting modest differences in the yield of newly diagnosed HIV infection across both recruitment strategies and testing approaches.

Among the approximately 108 female youth we expect to be newly diagnosed with HIV infection, about 20% are expected to successfully initiate HIV care at a health facility after a single SMS message. The remaining 80% (N=86) who are not linked to care after the initial SMS message will be randomly assigned to either continued SMS messages or to economic incentives. Assuming at least 60% are linked to care at some point during follow-up, survival analysis employing Cox regression will be able to detect a hazard ratio of 2.2 describing the impact of treatment condition (continued SMS vs. economic incentives) on the occurrence and timing of successful linkage to care at a health facility, with 80% power.

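### The second randomisation names no stratification by first-stage arm and the stage-2 Cox model names no first-stage term; adding the term is free and recovers a little power

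*Combined protocol and SAP*

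**What the plan says.** All of this is in the combined protocol and SAP.

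- **First stage.** Section 11.6.1: "We anticipate a total of 108 HIV positive participants to be randomly assigned to either standard referral or standard referral plus SMS at the first" randomisation. The Protocol Summary gives the arms as "standard referral (N≈54) or standard referral plus SMS message (N≈54").
- **Second stage.** Section 11.6.1: "Participants not linked to care after the first randomization will be re-randomized in a 1:1 ratio" to another SMS or an economic incentive.
- **Method.** Section 15.12: "We will utilize an approach called permuted blocks randomization for participant assignment to the intervention". Both sections describe "randomly ordered permuted blocks of either 2, 4, 6, 8 or 12 allocations". Neither names a stratification factor for either stage, nor says whether the second stage uses one list or one per first-stage arm.
- **Analysis.** Section 13.2: "Using the Cox Proportional Hazards Model, difference in the likelihood and timing of linkage between treatment conditions will be quantified" by a hazard ratio with an interval estimate. Table 1 likewise refers to two treatment conditions. No adjustment or stratification for first-stage arm is named. The paragraph on other analyses adds only exploratory predictors and interactions with participant characteristics.
- **Sample size.** Section 15.11: "about 20% are expected to successfully initiate HIV care at a health facility after a single SMS message", and "The remaining 80% (N=86) who are not linked to care after the initial SMS message will be randomly assigned" to continued SMS or incentives. It claims 80% power for a hazard ratio of 2.2 if at least 60% link. This text treats everyone as having had an SMS, although about half are randomised to referral alone.

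**The concern.** First-stage arm is itself randomised, is known at re-randomisation, and could plausibly predict later linkage. Permuted blocks balance the second-stage arms overall. Unless the list is split by first-stage arm, they do not balance first-stage composition within them. Adjustment in the analysis would deal with that, but none is named.

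At stake is some efficiency in the one stage-2 comparison that the plan powers, and the readability of a single small pilot result if an uneven split occurs. The validity of the randomised contrast is not at stake.

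**Working it through.** **1. The plan's own figure.** Non-linkers: 0.80 × 108 = 86.4, so 86. Events: 0.60 × 86 = 51.6. Schoenfeld's formula with 1:1 allocation and two-sided alpha 0.05 (an assumption, since alpha is not stated for this calculation):

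- Events needed = 4 × (1.96 + 0.84)² / (ln 2.2)² ≈ 51.
- Power at 51.6 events = Φ(√(51.6/4) × ln 2.2 − 1.96) = 80.8%.

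The stated 80% is reproduced.

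**2. Size of the chance imbalance.** If both first-stage arms lose 20% to linkage, each supplies 0.80 × 54 ≈ 43. With exact overall balance (43 per second-stage arm), the number from a given first-stage arm who receive the incentive is Hypergeometric(86, 43, 43):

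- mean 21.5, SD 2.33, 95% range 17 to 26;
- P(≤17 or ≥26) = 0.084.

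A 17:26 split is a difference in composition of 26/43 − 17/43 = 21 percentage points.

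A simulation of the whole process (10,000 trials, the plan's block sizes at both stages, 20% linked) agrees:

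| Second-stage list | SD of difference in first-stage share | 95th percentile of absolute difference | P(>20 points) | Smallest of the four cells: median (5th percentile) |
|---|---|---|---|---|
| Single list | 11 points | 22 points | 7% | 19 (15) |
| One list per first-stage arm | 2 points | 4 points | 0 | 20 (18) |

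With 10% and 30% linked in the two first-stage arms, the SD for a single list is still 11 points.

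**3. Effect on the estimate.** The shift in the log hazard ratio is approximately the difference in share × ln(first-stage hazard ratio). At 22 points it is 0.22 × ln 1.5 = 0.09, or 0.22 × ln 2.0 = 0.15. The standard error of the log hazard ratio is √(4/51.6) = 0.28, so these are about 0.3 and 0.5 of a standard error. Such shifts fall in either direction and average to zero.

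**4. Error rates.** Cox simulations: 4,000 trials per scenario, 86 participants, 43 per first-stage arm, about 60% events. The first-stage hazard ratios are assumptions.

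With no second-stage effect and a single list, the unadjusted test rejected in 4.2% to 5.4% of trials, with an average hazard ratio of 0.99 to 1.00.

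Power for a second-stage hazard ratio of 2.2:

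| First-stage HR (assumed) | Single list, unadjusted | Single list, adjusted | Separate lists, unadjusted | Separate lists, adjusted |
|---|---|---|---|---|
| 1.0 | 79.8% | 80.0% | 79.2% | 79.4% |
| 1.5 | 78.5% | 79.7% | 78.3% | 79.7% |
| 2.0 | 75.8% | 79.8% | 77.2% | 80.9% |

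The Monte Carlo standard error of one entry is about √(0.8 × 0.2/4000) = 0.6 points, so a repeat run can move entries by a point or so. In the last row, most of the loss comes from omitting the term and not from the list: separate lists without the term still give 77.2%. With a single list the unadjusted hazard ratio averages 2.14 against 2.25 adjusted. That is the usual pull towards 1 when a prognostic factor is left out of a Cox model.

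**The case against.** The strongest reply is that this hardly matters. The linkage study is a pilot under a secondary objective, the stated power is reproduced, and required events and sample size do not change. Even with a first-stage hazard ratio of 2.0, for which the documents give no support, separate lists gain only 77.2 − 75.8 = 1.4 points without the model term. All of that stands, and it is why the point is minor and the model term comes first.

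Four stronger readings are tempting, and the documents do not support them:

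- **That the second randomisation is unstratified.** The text is silent. It speaks of a list in the singular although there are two randomisations, so it cannot be taken literally, and separate lists are not ruled out. The figure of the adaptive design is not available in the text reviewed.
- **That the SMS-versus-incentive contrast is confounded with first-stage arm.** The second assignment is random whichever arm a girl came from. Chance imbalance is not bias, and type I error holds.
- **That stratifying would separate the effect of a first SMS from that of a second.** Girls from referral alone get their first linkage SMS at stage 2; the others get their second. A pooled hazard ratio averages the two even under perfect balance. Separating them needs an interaction or estimates within each first-stage arm.
- **That comparisons of the four sequences are damaged.** None is planned. Sections 13.2 and 15.11 address only the pooled contrast.

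**Conclusion.** The point holds as a minor omission. No stratification of the second randomisation by first-stage arm is stated, and the stage-2 Cox model does not use a factor that the trial itself randomises. The cost is about 4 points of power (75.8% against 79.8%) if the first-stage hazard ratio is 2.0, about 1 point at 1.5, and nothing at 1.0. There is no systematic bias and no inflation of type I error, and the plan's 80% figure is not overturned. These sizes rest on two-sided alpha 0.05, about 43 non-linkers per first-stage arm, 60% linkage overall, and assumed first-stage hazard ratios. The documents give 20% initial linkage only for a single SMS, and no first-stage effect.

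**What to change.** In section 13.2, pre-specify first-stage arm (referral alone or referral plus SMS) as a stratum or covariate in the stage-2 Cox model. This costs one model term and works even with a single allocation list.

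In sections 11.6.1 and 15.12, state whether the second-stage list is common or separate by first-stage arm. Separate lists are optional: they cost one extra list and add little once the term is in the model. Sample size, treatment and follow-up do not change.

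If the investigators also want to know whether a first and a second SMS act differently, they should add descriptive SMS-versus-incentive estimates within each first-stage arm. With about 43 girls per arm these would be imprecise.
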